7.5 Surgical Intervention

Approximately 3-4 weeks following completion of neoadjuvant chemotherapy a clinical assessment and repeat mammography and ultrasound will be performed. The patient will then proceed to breast and axillary surgery as judged by the treating physician. **Surgery should be performed approximately 3 - 4 weeks after the last dose of neoadjuvant ixabepilone or Ixabepilone plus cetuximab regimen** or at resolution of possible hematological or infective complication. Reasons for delaying surgery in individual patients must be recorded in source documentation.

8.0 CRITERIA FOR RESPONSE

8.0.1 PATHOLOGICAL RESPONSE: The histologic response after treatment will be evaluated in the primary tumor and in the axillary lymph nodes removed by axillary dissection. In the primary tumor, cellular modifications will be evaluated in both the infiltrating tumoral component and in the possible ductal component, if applicable:

- Analysis of the viable residual infiltrating component (% of total tumoral mass)

- Analysis of the residual ductal component (% of total tumoral mass)
- Determination of the mitotic index.

In the axillary lymph nodes: analysis of the viable residual component. The criteria of pathological response will be defined according to the Sataloff Classification ⁴⁶.

The response in the primary tumor site will be graded from A to D.

Primary site response:

T-A Total or near total therapeutic effect.

T-B Subjectively greater than 50% therapeutic effect but less than total or near total.

T-C Less than 50% therapeutic effect, but effect evident

T-D No therapeutic effect.

Axillary lymph node response:

N-A Evidence of therapeutic effect, no metastatic disease.

N-B No nodal metastasis or therapeutic effect.

N-C Evidence of therapeutic effect but nodal metastasis still

Present.

N-D Viable metastatic disease, no therapeutic effect

pCR corresponds to pathological grades T-A; N-A, N-B.

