Ixabepilone BMS-247550 CA163-157 Clinical Protocol

TMHRI IRB#0908-0265 BMS Protocol #: CA163-157

ICE Trial

RANDOMIZED OPEN-LABEL NEO-ADJUVANT PHASE II STUDY COMPARING IXABEPILONE (I) VS IXABEPILONE PLUS CETUXIMAB (IC) IN TRIPLE NEGATIVE BREAST CANCER PATIENTS (ICE)

VERSION: 8.0 DATE: 8/9/2012 PHASE: II IND Number: 104,307

[name]. Director, Methodist Cancer Center The Methodist Hospital/Weill Cornell University [name] [contact] [contact] [contact]

STUDY SUMMARY

Title:	Randomized open-label neo-adjuvant phase II study comparing					
	ixabepilone (I) vs. ixabepilone plus cetuximab (IC) in Triple negative breast					
	cancer patients					
Objectives:	Primary Objective:					
	1. To determine the pathologic complete response rate (pCR) (breast and					
	axilla) of Ixabepilone versus Ixabepilone when combined with cetuximab					
	in patients with invasive breast adenocarcinoma T1N1-N3M0 or					
	T2-4 N0-3M0 disease who are Triple negative and who are candidates for					
	preoperative chemotherapy.					
	Secondary Objective(s):					
	1. To evaluate overall objective response rate in both treatment groups.					
	2. To assess toxicity of each regimen.					
	Exploratory Objectives:					
	1. To correlate the expression of biomarkers such as PTEN, EGFR					
	and EGFR-pathway associated genes (including, but not limited to,					
	TGF- α , CRYAB, NRAS, KRAS, AKT3, PTEN, MEK1 and KRAS					
	amplicon genes) with the objective clinical and pathologic response.					
	2. To potentially explore other gene/protein expression patterns,					
	mutations and gene/chromosomal copy number alterations related					
	to sensitivity or resistance to ixabepilone, other anti-microtubule					
	agents and cetuximab. These additional exploratory analyses may					
	include, but are not limited to, beta tubulin isoforms, ABC					
	transporters, TACC3, HCAPG, GTSE1, Kallikreins and defined					
	gene models associated with ixabepilone response.					

Study	-Patients with either T1N1-N3M0 or T2-4 N0-3M0 disease who are Trip				
population:	on: negative and who are candidates for preoperative chemotherapy.				
Sample	116 patients.				
Size:					
Number of	Single Institution: The Methodist Hospital Research Institute.				
Centers:					
Treatment	This is a randomized open-label phase II trial; 116 triple negative breast				
Plan:	cancer patients will be randomized equally between 1) Ixabepilone or				
	2) Ixabepilone plus Cetuximab.				

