given in a dose of 40 mg/m² as a 3-hour IV infusion every 3 weeks. A total of 161 subjects were treated. Median age was 55 years. Results in evaluable subjects were Primary Best Overall Response Rate (Complete Response [CR] or Partial Response [PR]): 98/161 (61%); Pathologic Complete Response in Breast [pCR_B]: 29/161 (18%); and Pathologic Complete Response in Breast and Lymph Nodes [pCR_{BL}]: 17/161 (11%). Independent assessment of subject responses yielded pCR_B and pCR_{BL} rates of 14% and 9%, respectively. In subjects with ER-negative, ER-/PR-negative, and triple-negative tumors, as assessed by locally read immunohistochemistry (IHC) and fluorescence in situ hybridization (FISH), investigator-assessed pCR_B rates were 29%, 33%, and 26%, respectively. The pCR_{BL} rates were 19%, 23%, and 19%, respectively.

No deaths were reported. Twelve (8%) subjects reported SAEs. Among these subjects, 10 (6%) reported at least 1 SAE assessed as possibly, probably, or certainly related to ixabepilone therapy. These SAEs included peripheral or sensory neuropathy, febrile neutropenia, neutropenia, vomiting, and hypersensitivity, each reported in 2 subjects; and mucositis, constipation, diarrhea, stomatitis, lymphopenia, leukopenia, thrombocytopenia, increased ALT, and increased AST, each reported in 1 subject.

Treatment-related adverse events were reported in 97% of subjects. The most common (\geq 15% of subjects) were alopecia (86%), myalgia (50%), arthralgia (30%), asthenia (27%), neutropenia (21%), peripheral sensory neuropathy (20%), nausea (19%), fatigue (19%), and diarrhea (15%). Most were Grade 1 to 2. Grade 3/4 treatment-related adverse events were reported in 25% of subjects. The most common Grade 3/4 event was neutropenia (14%).¹²

CA163-081: Phase 2 Study in Refractory MBC

CA163-081 was a single-arm, open-label, multicenter, multinational, two-stage design study of ixabepilone in MBC that was resistant to an anthracycline, a taxane, and capecitabine. A total of 126 subjects were treated. Data from this study have been published. Of the 126 treated subjects, 113 were evaluable for response. Subjects were heavily pretreated: 88% had received \geq 2 lines of prior chemotherapy in the metastatic setting. Independent Radiology Facility (IRF)-

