7.0 Treatment Plan/Methods

This is a randomized open-label phase II trial; 116 triple negative breast cancer patients will be randomized equally between 1) Ixabepilone or 2) Ixabepilone plus Cetuximab. The study population will include patients≥ 18 years of age diagnosed with invasive mammary carcinoma. Patients will be assigned to treatment arms using a stratified blocked randomization, with strata based on disease stage (T1N1-3M0 or T2-4 N0-3M0). All patients will receive a physical assessment, imaging, a blood draw, and a core needle biopsy (CNB) a biopsy prior to the start of treatment.

7.1 Treatment Arm 1

Patients will receive Ixabepilone 40mg/m² given over approximately 3-hours on day 1 Patients will receive a total of four cycles of this combination with each cycle given 21(+/- 3) days.

Subjects will be premedicated approximately 1 hour before the ixabepilone infusion with either 1) both an oral H1 blocker (diphenhydramine 50 mg or equivalent) and an oral H2 blocker (e.g., ranitidine 150 300 mg or cimetidine 300–800 mg or nizatidine 150-300 mg or famotidine 20–40 mg); or 2) with premedication per institutional standards. Premedication with steroids is indicated in subjects who developed a hypersensitivity reaction to ixabepilone in previous cycles. Patients with severe reaction should not be retreated (see dose modification chart below).

7.2 Treatment Arm 2

Patients will receive Ixabepilone 40mg/m^2 given over approximately 3-hours on day 1 followed by Cetuximab given on day 1 at 400 mg/m² as an initial loading dose (first infusion) administered as a 120-minute IV infusion (maximum infusion rate 5 mL/min) followed by 250 mg/m² infused over 60 minutes (maximum infusion rate 5 mL/min) as a subsequent weekly dose. Patients will receive a total of 4 cycles of this combination with each cycle being 21 (+/-3) days.

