8.0.2 RECIST Criteria

The main endpoint in this study is to determine the pathologic complete response rate (pCR) (breast and axilla) of Ixabepilone versus Ixabepilone when combined with cetuximab in patients with invasive breast adenocarcinoma T1N1-N3M0 or T2-4 N0-3M0 disease who are Triple negative and who are candidates for preoperative chemotherapy.

The clinical tumor response will be assessed using RECIST criteria at baseline and before surgery.

RECIST criteria offer a simplified, conservative, extraction of imaging data for wide application in clinical trials. They presume that linear measures are an adequate substitute for 2-D methods and register four response categories⁴⁷:

- CR (complete response) = disappearance of all target lesions
- PR (partial response) = 30% decrease in the sum of the longest diameter of target lesions
- PD (progressive disease) = 20% increase in the sum of the longest diameter of target lesions
- SD (stable disease) = small changes that do not meet above criteria
 9.0 Study Materials:

Chemistry

The epothilones are a class of tubulin polymerization agents obtained from the fermentation of *Sorangium cellulosum*. Ixabepilone is a semisynthetic derivative of epothilone B that has improved in vitro metabolic stability when compared with its natural precursor.

Pharmaceutical Properties and Formulation

Investigational Product Identification

Ixabepilone for Injection

Ixabepilone is a 16-membered polyketide macrolide, with a chemically modified lactam substitution for the naturally existing lactone. The chemical name for ixabepilone is $[1S-[1R^*,3R^*(E),7R^*, 10S^*,11R^*,12R^*,16S^*]]$ -7,11-dihydroxy-8,8,10,12,16-pentamethyl-3-[1-methyl-2-(2-methyl-4-thiazolyl)ethenyl]-17-oxa-4-azabicyclo[14.1.0]heptadecane-5,9-dione. It has a molecular formula of C₂₇H₄₂N₂O₅S, and its molecular weight is 506.71 grams/mole.

Ixabepilone for Injection is supplied as a lyophilized (freeze dried), white to off-white, whole or fragmented cake in a vial. The drug product is available in two potencies:

- Ixabepilone, for injection 15 mg supplied with diluent for ixabepilone, 8 mL.
- Ixabepilone, for injection 45 mg supplied with diluent for ixabepilone, 23.5 mL.

Vehicle for Constitution of Ixabepilone for Injection

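### The protocol does not state that the pathologist who assigns the pCR grade is masked to treatment arm, although the grade turns on a judged border in an open-label, single-centre trial

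*Combined protocol and SAP*

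**What the plan says.** The primary endpoint is pCR in breast and axilla (Sections 1.1 and 8.0.2). Section 8.0.1 defines it by Sataloff grades: "pCR corresponds to pathological grades T-A; N-A, N-B". The two breast grades on either side of the cut are "T-A Total or near total therapeutic effect", which qualifies, and T-B, "Subjectively greater than 50% therapeutic effect" but short of T-A, which does not. The same section asks for the residual infiltrating and ductal components as percentages of the tumour mass, and for the mitotic index, but ties none of these to a grade.

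Section 7.0 states: "This is a randomized open-label phase II trial". The Study Summary gives the number of centres as "Single Institution: The Methodist Hospital Research Institute".

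On who reads the specimen, the protocol is silent. It names no reader, does not say whether the reader knows the arm, and provides no second reading. The central laboratory receives slides for biomarker work only (Section 2.0 footnote j; Sections 2.2, 2.5 and 3.0.1). The one blinded review in the document is the radiology review of another trial, CA163-046 (Section 4.0.2). A laboratory manual and a procedure manual are cited but were not available.

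**The concern.** A graded endpoint can be biased between arms when three things coincide: the grade involves judgement, the reader can learn the treatment, and nothing separates the two. The protocol shows the first, leaves the second open, and does not address the third. If a reader who knows that a patient had the combination resolves doubtful T-A/T-B cases upwards more often, the primary comparison is inflated. Neither intention-to-treat analysis (Section 12.2) nor a larger sample would correct that.

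The protocol's own background shows that the reader matters. In CA163-080, the source of the planned control rate, investigators reported pCR of 18% in the breast and 11% in breast and nodes. Independent assessment gave "rates of 14% and 9%, respectively".

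**Working it through.** **Inputs.** Section 12.1: 54 patients per arm, control pCR 18%, combination pCR 43%, two-sided 0.05, power 81.9%. Section 12.2: Cochran-Mantel-Haenszel test. Section 4.0.2: the CA163-080 reading rates. The documents give no stratum sizes, so the check is unstratified.

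**Step 1: reproduce the planned power.** With x1 and x2 responders in the two arms and p̄ = (x1 + x2)/108,

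z = [(x2 − x1)/54] / √[p̄(1 − p̄) × 2/54].

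The rejection probability is the sum of Bin(x1; 54, p1) × Bin(x2; 54, p2) over all pairs with |z| ≥ 1.96. For 18% v 43% this gives 81.9%, as stated. For 45% and 47% it gives 87.0% and 91.0%, and for 49% it gives 94.05% against the 94.0% in Table 1. (The table's entries 0.43% to 0.49% are read as 43% to 49%.)

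**Step 2: the reader gap in CA163-080.** Breast: 29/161 = 18% by investigators. Independent: 0.14 × 161 = 22.5, so about 23 patients, a gap of 4 points or about 6 patients. Breast and nodes: 17/161 = 11% against 0.09 × 161 = 14.5, a gap of 2 points.

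**Step 3: effect of one-sided upgrading (assumed range).** Let true pCR be 18% in both arms, and let a share u of true non-responders be upgraded in the combination arm only. The observed combination rate is p2 = 0.18 + 0.82u, and the expected number upgraded is 54 × 0.82u.

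| u | p2 | Patients upgraded | Two-sided rejection | In favour of combination |
|---|---|---|---|---|
| 0 | 18.0% | 0 | 5.0% | 2.5% |
| 2% | 19.6% | 0.9 | 5.6% | 4.1% |
| 5% | 22.1% | 2.2 | 8.3% | 7.7% |
| 10% | 26.2% | 4.4 | 17.7% | 17.5% |

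If a whole CA163-080 gap fell on the combination arm alone, two-sided rejection would be 5.9% (2 points) or 8.2% (4 points).

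**Step 4: the same leniency in both arms.** With u = 5% in each arm, 18% v 43% becomes 22.1% v 45.9%. Power by the pooled normal approximation falls from 81.5% to 74.8%. That costs power but does not create a false advantage for either arm.

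**The case against.** Several arguments on the other side are sound and limit the point.

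- **Missing statement, not shown exposure.** A reader might infer that nothing hides the arm, or that the pathologist knows it. The documents do not support either. They do not say who grades or what that person is told, and the cited manuals might already cover it.
- **The endpoint is not one free judgement.** Section 8.0.1 asks for residual percentages and the mitotic index, and the nodal part depends mainly on whether metastasis is present. A doubtful breast grade changes pCR only in a patient whose nodes are clear. This narrows the exposure but does not remove it, because pCR always requires T-A and no percentage defines it.
- **CA163-080 is not evidence of bias between arms.** It had one arm. The protocol does not say that it used the T-A/T-B border or that its independent assessors were masked. It shows reader dependence only.
- **A single grade deciding the trial is a knife-edge picture.** By the unstratified Mantel-Haenszel test, 10/54 v 19/54 gives p = 0.052 and 10/54 v 20/54 gives p = 0.032. Every binary endpoint has such a pair. At the planned rates (about 10 v 23), p = 0.007, and four responders must be lost before significance goes. Starting from 10 v 10, ten of 44 non-responders must be upgraded in one arm to reach it.
- **Masking will be imperfect.** A reader with access to the hospital record can find the arm.

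What remains is a plausible and avoidable route to bias in the primary comparison, and a safeguard that costs little.

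**Conclusion.** The point holds as a cheap improvement. The protocol makes pCR depend on a judged border, runs open-label at one institution, and does not state that the reader is masked. It does not show that grading is biased.

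The size is conditional. With true pCR of 18% in both arms, upgrading confined to the combination arm, 54 per arm and no stratification, the two-sided false-positive rate moves from 5.0% to 5.6%, 8.3% or 17.7% as 2%, 5% or 10% of non-responders are upgraded. The upgrading shares are assumptions, since the documents offer no arm-specific figure. Small lapses do little harm, while consistent leniency on about four patients would more than triple the error rate.

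**What to change.** Add to Section 8.0.1:

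> Surgical specimens are sent for study grading under the study number; the request form states that neoadjuvant therapy was given but not the arm. The pathologist who assigns the T and N grades does not consult the treatment record, and the grades are recorded and locked before the arm is disclosed.

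The pathologist who already reads the specimen can do this. If a manual already contains such a step, a sentence in Section 8.0.1 pointing to it is enough.

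**Cost.** Minor administration: a request form for study grading and a record of when the grades were locked. Enrolment (116), the analysed number (108) and the nominal power (81.9%) stay as they are.

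**Limits.** The hospital record still shows the arm, so the safeguard relies partly on the reader keeping to it. Masking also leaves the near-total limit undefined. It stops knowledge of the arm from steering doubtful calls but does not make the border sharper. Tying T-A to the residual percentages already recorded would be a useful separate clarification.

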10.1 Common side effects of Ixabepilone65	
10.2 Common side effects of cetuximab71	1
10.3 Reporting of SAEs73	3
11. Data Management70	6
12. Statistical Design and Analyses70	6

1	I3. Reference/Bibliography	79
	12.3 Interim data analysis	.78
	12.2 Statistical analysis	.77
	12.1 Sample size estimate	.76

1.0 Synopsis:

Ixabepilone and capecitabine combination has demonstrated to be an active regimen in patients with metastatic breast cancer (MBC) after failing an anthracycline and a taxane regimen. Cetuximab is active in tumors that express EGFR with demonstrated activity in head and neck and colorectal tumors. A proportion of breast cancers are known to express EGFR. Cetuximab's mechanism of action suggests the possibility of efficacy in breast cancer patients and several studies show that it may be efficacious in Triple Negative Breast Cancer (TNBC). This study seeks to evaluate Ixabepilone alone or in combination with cetuximab as a possible way to increase antitumor activity.

This is a randomized open-label phase II trial, one hundred sixteen triple negative breast cancer patients will be randomized equally between 1) Ixabepilone or 2) Ixabepilone plus Cetuximab. Randomization will be stratified by disease stage (T1N1-3M0 or T2-4 N0-3M0).

At the baseline all patients will receive a physical assessment, imaging, a blood draw, and a biopsy prior to the start of treatment.

1.1 Primary Objective(s):

To determine the pathologic complete response rate (pCR) (breast and axilla) of Ixabepilone versus Ixabepilone when combined with cetuximab in patients with invasive breast adenocarcinoma T1N1-N3M0 or T2-4 N0-3M0 disease who are Triple negative and who are candidates for preoperative chemotherapy.

1.2 Secondary Objective(s):

To evaluate overall objective response rate in both treatment groups.

To assess safety and toxicity of each regimen.

1.3 Exploratory Objective(s):

To correlate the expression of biomarkers such as PTEN, EGFR and EGFRpathway associated genes (including, but not limited to TGF- α , CRYAB, NRAS, KRAS, AKT3, PTEN, MEK1 and KRAS amplicon genes) with the objective clinical and pathologic response.

For all samples available, the following tests will be conducted:

- Immunohistochemical detection of EGFR, and the PTEN expression in tumor tissue samples. For those EGFR-pathway associated genes (including, but not limited to, TGF-α, CRYAB, NRAS, KRAS, AKT3, PTEN, MEK1 and KRAS amplicon genes) an mRNA-based assay will be used.

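### The primary endpoint is called pathologic complete response, but the only scoring rule also counts near-total breast responses with clear nodes as complete

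*Combined protocol and SAP*

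**What the plan says.** The Study Summary, section 1.1 and section 8.0.2 all name the endpoint in the same terms. Section 8.0.2 reads: "The main endpoint in this study is to determine the pathologic complete response rate (pCR) (breast and axilla").

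Section 8.0.1 turns pathology into that endpoint. It relies on a published classification ("The criteria of pathological response will be defined according to the" Sataloff system, reference 46), lists the breast and nodal grades, and closes with "pCR corresponds to pathological grades T-A; N-A, N-B".

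- The top breast grade is "T-A Total or near total therapeutic effect".
- The next is "T-B Subjectively greater than 50% therapeutic effect but less than total or near total".
- N-A and N-B both mean no nodal metastasis. N-C and N-D mean that nodal disease remains, and neither counts as pCR.

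The same section requires two measurements in the breast: "Analysis of the viable residual infiltrating component (% of total tumoral mass") and "Analysis of the residual ductal component (% of total tumoral mass"). Neither is linked to pCR.

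Sections 12.1 and 12.2 use pCR without defining it again. Section 12.1 plans on 18% for Arm 1, citing study CA163-080.

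**The concern.** Name and rule differ in strictness, and only on the breast side. A reader who meets the reported pCR rate will take it to mean no residual disease in breast or axilla. Under 8.0.1 the rate can include patients whose breast response was near-total and so not complete.

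Two further gaps sit at the same boundary. The protocol reproduces no threshold for near total. It also does not say whether a patient with residual ductal disease and no infiltrating tumour has a pCR, although it asks for the ductal percentage.

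At stake is what the primary rate means, and whether it can be set beside the planning rate, whose own pCR criteria are not given. The planning rate also has a mismatch of its own in site and population, which is smaller and does not depend on how T-A is defined.

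**Working it through.** **1. Does any text exclude near-total responses from pCR?**

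- Name (Study Summary, 1.1, 8.0.2): complete response, breast and axilla.
- Rule (8.0.1): T-A together with N-A or N-B.
- T-A covers total and near-total effect. T-B lies below both. A near-total breast response can therefore only be graded T-A.
- With N-A or N-B it is scored as pCR. The nodal half of the rule is strict; the breast half is not.
- Sections 12.1 and 12.2 contain no other definition, and the residual percentages in 8.0.1 carry no pCR cut-off.

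Following the plan exactly thus reports some non-complete breast responses as complete. How many is not given.

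**2. Reproducing the plan's power.** Inputs from 12.1: 54 per arm, 18% versus 43%, two-sided 0.05.

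Normal approximation with pooled variance under the null: mean rate p = (0.18 + 0.43)/2 = 0.305.

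z = [0.25 − 1.96·√(2·0.305·0.695/54)] / √[(0.18·0.82 + 0.43·0.57)/54] = (0.25 − 0.1737)/0.0853 = 0.895, so power is 81.5%.

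Exact power sums the two binomial distributions over all tables that the uncorrected chi-square test rejects. Applying the Mantel-Haenszel factor (N−1)/N, without strata, leaves the value unchanged. It gives 81.9%, the stated figure. Exact power is used below.

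**3. Can a power effect be attached to the T-A rule?** It would need the near-total share in each arm, which the documents do not give. Assumed values show how far the answer depends on them:

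| Assumption (illustration only) | Arm 1 | Arm 2 | Power |
|---|---|---|---|
| Plan as stated | 18% | 43% | 81.9% |
| 5 points added to both arms | 23% | 48% | 79.1% |
| 10 points added to both arms | 28% | 53% | 76.0% |
| 20% of strict non-responders added in Arm 1 only (0.18 + 0.82·0.20) | 34.4% | 43% | 15.1% |
| 20% of strict non-responders added in Arm 2 only (0.43 + 0.57·0.20) | 18% | 54.4% | 98.4% |

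All rows also take 18% and 43% as strict rates, which the documents do not say. Neither the direction nor the size can be determined.

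**4. The planning rate.** Section 4.0.2 (CA163-080) gives:

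- breast only, all subjects: 29/161 = 18%;
- breast and nodes, all subjects: 17/161 = 11%;
- breast and nodes, triple-negative: 19%, listed after investigator-assessed subgroup rates, with no denominator.

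The 18% in 12.1 equals the first of these. The endpoint and population of this trial match the third. Exact power at 54 per arm:

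- 19% versus 44% (25-point difference kept): 81.2%;
- 19% versus 43% (Arm 2 rate kept): 78.2%.

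**The case against.** The rule is not hidden. Section 8.0.1 names its classification, prints every grade and says which ones count, so the endpoint is prespecified. The cited source may bound near total more tightly than the protocol does, and that cannot be checked from the documents. Both points stand. They limit the criticism to what the protocol itself says, but they do not remove the difference between name and rule.

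A second objection is that requiring 0% residual infiltrating tumour replaces the primary endpoint in a version 8.0, open-label protocol. That is fair. It is why keeping the T-A rule under an accurate name is offered as an equal option.

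A reader might go further and infer that the treatment comparison is biased or that the trial is underpowered. The documents support neither. Nothing in them suggests that grading differs between arms. Without a near-total share, the power figures in step 3 reflect only what is assumed. Nor does the mismatch in the 18% show that the sample size fails, since the matching rate is one point higher and power at the planned difference stays above 80%.

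**Conclusion.** The point holds as a fault in the meaning of the primary rate. As written, 8.0.1 reports near-total breast responses with clear nodes as pathologic complete responses, and leaves the near-total threshold and the status of residual ductal disease unstated in the protocol. This should be fixed, but it does not invalidate the test: the comparison of arms remains valid on the condition that grading is the same in both.

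The inflation of the reported rate over a strict pCR rate cannot be quantified from the documents.

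The planning-rate correction is minor: 0.7 points of power (81.9% to 81.2%) if the 25-point difference is kept, or 3.7 points (81.9% to 78.2%) if Arm 2 is held at 43%. Both figures assume that the 19% was obtained under pCR criteria comparable with this trial's, which the documents do not state.

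**What to change.** Make name and rule agree before arms are compared, in one of two ways.

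(a) In 8.0.1, define primary pCR as 0% viable residual infiltrating tumour in the breast plus N-A or N-B, and state whether residual ductal disease is allowed. In 12.2, report the rate of T-A with N-A or N-B as a secondary result.

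(b) Keep the T-A rule, rename the endpoint complete or near-complete pathologic response in the Study Summary, 1.1 and 8.0.2, write the near-total cut-off and the position on ductal disease into 8.0.1, and report the strict 0%-residual rate alongside.

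Separately, in 12.1 restate the control rate as 19% (triple-negative, breast and nodes), give power of 81.2% for 19% versus 44% and 78.2% for 19% versus 43%, and note that the pCR criteria behind the 19% are not given.

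Cost: wording only, with no new measurement, because 8.0.1 already requires the residual percentages. At the planned 25-point difference the corrected control rate does not call for more patients. The strict pCR rate may be somewhat lower than the T-A rate. Enrolment status is not stated; any specimens already graded would have to be re-classified from the recorded percentage.
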